2.1 STUDY DESIGN

Observational, retrospective, multicentre study in spanish patients with metastatic Renal Cell Carcinoma (mRCC) treated with sunitinib as a first-line treatment (treatment with previous cytokine therapy is accepted) according to clinical practice who obtained a complete response (CR) to treatment in one of these 2 situations:

- a) Complete response (CR) obtained exclusively with first-line sunitinib treatment (sunitinib CR).*
- b) Response obtained after a period of time on treatment with sunitinib in which local treatment was also performed (surgery of the residual metastasis/metastases, radiofrequency ablation or radiotherapy) to achieve the total macroscopic disappearance of the disease, according to the opinion of the physician responsible for the patient (CR + local treatment).*

The patient population eligible for this study includes any patient with advanced or metastatic renal cancer treated with Sunitinib and who has achieved a CR to the tumour and its metastases at some point in the treatment and according to the usual evaluation criteria in daily clinical practice irrespective of whether it was obtained with Sunitinib alone or local treatment was required to eradicate all lesions: (residual metastasis(es), radiofrequency ablation or radiotherapy)

The requirements for a patient's inclusion are that:

- 1. These patients must have Sunitinib as first-line treatment in accordance with its Summary of Product Characteristics.*
- 2. Collection of clinical, safety and response data in patients with advanced kidney cancer.*

The study is expected to be conducted in at least 50 sites throughout Spain in order to reach the maximum number of study patients.

Case collection will start at each site after the contract with the site has been signed, all the study documentation is available and training in the procedures and objectives of the protocol has been provided by the person appointed by the sponsor.

Any number of patients that meet the inclusion criteria and no exclusion criteria may be recruited at the site.

This is an observational study designed to reflect routine clinical practice; there will be no interference with the daily routine of the medical care provided to kidney cancer patients.

The data collected will correspond to those usually collected in the medical record; patient demographic variables (never personal data that could lead the patient to be identified), age at start of treatment, routine laboratory values required in the diagnosis and control of this pathology, patient functional status and clinical status. Treatment compliance, tolerability and adverse events and treatment effectiveness will be collected.

Since this is an observational study, no additional material not provided for in routine practice will be required.

Any patient who meets the inclusion criteria and who does not meet any of the exclusion criteria and has received treatment with Sunitinib prior to participation in the registry will be considered evaluable.

No patient follow-up period is established and nor is there any interview with them, since there is only one moment in which the patient's data are reviewed; this will be when the investigator completes the case report form.

Analysis population

Patients above the age of 18 years with advanced carcinoma with a renal cell component who have received Sunitinib as a first line of treatment according to the indication of the drug and who have achieved a CR according to the criteria of the responsible medical team will be included.

During the study recruitment period, the participating sites may include all patients who meet the study's inclusion criteria and do not meet any of the exclusion criteria.

Since this is an observational and exploratory study, no hypothesis has been established and the number of subjects included will not be pre-established, although a sample of close to 90 cases is estimated in around 50 Spanish sites.

Treatment with Sunitinib will have begun before the patient is included in this registry, hence the treatment decision will depend solely on the treating physician's clinical criteria.

[figure not shown]
2.2 STUDY OBJECTIVES

Describe the complete responses in daily clinical practice in Spain in the 2007-October 30, 2018 period as the documented disappearance of all lesions in the investigator's opinion on at least 2 consecutive CT scans.

Seek associations between the CR from the macroscopic point of view and the baseline features of both patient and tumour, such as:

- Demographic characteristics (age at the start of treatment)
- Comorbidities: cardiovascular, renal, endocrine, autoimmune, intestinal, chronic dermatological, obesity, intestinal and hepatic.
- Previous nephrectomy
- Classification of the risk group according to Motzer and/or Heng criteria and of the association between each one of the prognostic variables, such as: patient baseline status, time elapsed from nephrectomy to the start of systemic treatment, presence of anaemia, corrected calcium, LDH levels, neutrophil and platelet levels.
- Tumour data: histology, Fuhrman grade, presence of tumour necrosis and number and location of metastases (organs involved).

PFIZER CONFIDENTIAL

The risk factors associated with the occurrence of CR from the macroscopic point of view will be sought.

SECONDARY OBJECTIVES

- *Develop recommendations to be followed in patients who obtain CR when treated with Sunitinib based on the case registry and the therapeutic strategy adopted that yielded the greatest clinical benefit.*
- *Define the median time of treatment with Sunitinib until complete remission of the lesions in the opinion of the patient's treating physician.*
- *Define the median duration of the CR.*
- *The time elapsed from the verification of the CR to disease to stabilisation/progression or change of treatment due to unacceptable toxicity or death from any cause will be collected.*
- *A record of the doses and treatment regimens used will be made. In the event of changes in the treatment dose (increase or reduction) the reason will be specified: toxicity, efficacy, decision taken after the disappearance of lesions or at patient's request.*
- *Description of local treatment techniques if used and when they were applied. In the pathological anatomy report of the resected piece, the percentage of necrosis and histology will be recorded, as will any surgical complications that presented.*
- *Safety profile of treatment with sunitinib: the highest grade adverse events presented by the patients will be recorded, as well as whether the treatment had to be discontinued at any point due to toxicity.*
- *In cases of discontinuation of systemic treatment after a period of treatment with maintained CR, the reason for the decision and the patient's participation in this decision (whether the patient was consulted, whether it was at the patient's request or the investigator's decision).*
- *Pharmacological group by mechanism of action used in patients in the second line after disease progression: another TKI, treatment with a drug acting on the immune system.*

Exploratory analysis:

[figure not shown]
Baseline neutrophil/leukocyte ratio and evolution of the neutrophil/lymphocyte ratio throughout treatment; at 4-6 weeks, 3 months, 6 months, 9 months, 12 months and then every 6 months in the available analyses close to these dates.

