NON-INTERVENTIONAL (NI) STUDY PROTOCOL

Study Information

Title	REGISTRY OF COMPLETE RESPONSES TO SUNITINIB IN SPANISH PATIENTS WITH METASTATIC RENAL CELL CARCINOMA (ATILA STUDY)
Protocol Code	A6181227
Protocol Version	Version 1.0 of 18 th October 2018
Date of the latest Protocol version	18 th October 2018
Active substance	Sunitinib Malate
Drug	SUTENT®
Objectives of the registry:	
To identify patients with metastatic renal cell carcinoma (mRCC) who obtained complete response (CR) to treatment with sunitinib alone or with sunitinib and a local treatment to eliminate residual disease and achieve CR in the clinician's opinion.
 
The clinical baseline characteristics of these patients and the tumour will be described in order to find predictive factors of response.
 
The aim is to describe the therapeutic strategy adopted in patients who obtained greater clinical benefit in the cases described once the macroscopic lesions have been eradicated in order to draft recommendations to follow once the statistical analysis of the registry is available.

PFIZER CONFIDENTIAL

Authors:

PPD MD PhD

Medical Oncologist

PPD

PPD MD

Senior Medical Advisor GU Pfizer

PPD

Pfizer Oncology Medical Department

Tel.: PPD

Email: PPD

This document contains confidential information belonging to Pfizer. Unless otherwise agreed in writing, on accepting or reviewing this document, you agree to keep this information confidential and not to copy it or disclose it to others (except when required by applicable law) or to use it for unauthorised purposes. In the event of any actual or suspected non-compliance with this obligation, Pfizer should be promptly notified.

TABLE OF CONTENTS

TABLE OF CONTENTS.....	3
1. LIST OF ABBREVIATIONS.....	5
2. PERSONS RESPONSIBLE FOR THE STUDY	9
3. ABSTRACT.....	10
4. AMENDMENTS AND UPDATES.....	16
5. MILESTONES.....	16
6. STUDY RATIONALE	17
7. HYPOTHESIS AND OBJECTIVES	26
7.1. Primary objectives:.....	26
7.2. Secondary objectives:.....	27
7.3. Exploratory analysis:.....	28
8. METHODS OF INVESTIGATION.....	28
8.1. Study design.....	28
8.2. Scope	29
8.2.1. Inclusion Criteria	30
8.2.2. Exclusion Criteria	30
8.3. Variables.....	31
8.4. Source documents.....	33
8.5. Sample size.....	33
8.6. Treatment of data.....	34
8.6.1. Case Report Forms (CRFs)/Data Collection Tools (DCTs)/Electronic Data Record.....	34
8.6.2. Records preservation.....	34
8.7. Data analysis	35
8.8. Quality control.....	35
8.9. Research methods limitations.....	36

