3. ABSTRACT

Observational, retrospective, multicentre study in spanish patients with metastatic Renal Cell Carcinoma (mRCC) treated with sunitinib as a first-line treatment (treatment with previous cytokine therapy is accepted) according to clinical practice who obtained a complete response (CR) to treatment in one of these 2 situations:

- a) Complete response (CR) obtained exclusively with first-line sunitinib treatment (sunitinib CR).
- b) Response obtained after a period of time on treatment with sunitinib in which local treatment was also performed (surgery of the residual metastasis/metastases, radiofrequency ablation or radiotherapy) to achieve the total macroscopic disappearance of the disease, according to the opinion of the physician responsible for the patient (CR + local treatment).

This is a retrospective registry of spanish patient cases, from the drug marketing in 2007 to 30th October 2018.

Since the Summary of Product Characteristics for sunitinib does not provide indications to be followed in patients with complete remission of the disease, there is an open debate on whether they should continue with the treatment for life, with the toxicity that this entails, or by contrast, whether sunitinib should be considered permanently discontinued after a certain time period (also under discussion).

Cases have been reported in which, after a treatment period with the patient in complete remission, it was decided to discontinue the treatment and patients continue being disease free for years. Could we talk about a cure in these cases? What would the definition of CR be?

- **Primary study objectives:**

To describe complete responses in daily clinical practice in Spain between 2007 and 30 October 2018, such as the documented disappearance of all lesions of advanced renal cell carcinoma according to the investigator's criteria in at least 2 consecutive CT (Computerised axial tomography) scans.

To look for associations between CR from a clinical point of view and the baseline characteristics of both the patient and the tumour, such as:

- Demographic data (age at the start of treatment)
- Previous nephrectomy
- Classification of the risk group according to Motzer and/or Heng criteria and the association between each prognostic variable, such as: baseline patient status, time from nephrectomy to systemic treatment start, presence of anaemia, corrected calcium, LDH (lactate dehydrogenase) levels, neutrophil levels and platelet levels.

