7. HYPOTHESIS AND OBJECTIVES

This study is a retrospective registry of cases of CR to treatment with sunitinib in patients with metastatic renal cell carcinoma and has a purely descriptive purpose. Therefore, no previous hypothesis has been established.

7.1. Primary objectives:

To describe complete responses in daily clinical practice in Spain between 2007 and 30 October 2018, such as the documented disappearance of all lesions in the investigator's opinion on at least 2 consecutive CT scans.

To look for associations between CR from a macroscopic point of view and the baseline characteristics of both the patient and the tumour, such as:

- Demographic characteristics (age at the start of treatment)
- Comorbidities: cardiac, renal, endocrine, autoimmune and liver.
- Previous nephrectomy

- Classification of the risk group according to Motzer and/or Heng criteria and the association between each prognostic variable, such as: baseline patient status, time from nephrectomy to systemic treatment start, presence of anaemia, corrected calcium, LDH levels, neutrophil levels and platelet levels.
- Tumour data: histology, Fuhrman grade, presence of tumour necrosis and number and location of metastases (organs involved).

7.2. Secondary objectives:

- **To establish recommendations** to be followed **in patients who obtain CR to sunitinib treatment** based on the case recording and the adopted therapeutic strategy that obtained the greatest clinical benefit.
- To define **the median time on treatment with sunitinib until lesion complete remission is reached in the patient responsible physician opinion.**
- To define **the median duration of CR.**
- The time elapsed from the confirmation of CR to disease stabilisation/progression or change of treatment due to unacceptable toxicity or death from any cause will be collected.
- **The dose and treatment regimens used will be recorded.** In the case of changes in the treatment dose (increase or reduction), the reason (toxicity, efficacy, decision taken after lesion elimination or upon request of the patient) will be specified.
- **Description of local treatment techniques** if they were used and at what time they were applied. In the case of a pathology report on the resected part, the percentage of necrosis and histology will be recorded, as well as the surgical complications in the case that they arose.

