8.2.1. Inclusion Criteria

Patients must meet all the inclusion criteria described below to be eligible for the study:

1. Patients who are 18 year-old or over who have been treated for metastatic renal cell carcinoma with sunitinib as first-line treatment (treatment with prior cytokine therapy is accepted) between 2007 and 30 October 2018 and who have obtained as a best treatment response the total remission of the disease in the opinion of the doctor in charge from a clinical, radiological and/or macroscopic point of view. This response must have been reached through two possible strategies:
 - A) Systemic treatment with sunitinib alone.
 - B) Treatment with sunitinib and subsequent local treatment for one or more residual lesions that have not responded to the drug (traditional surgery, radiotherapy, SBRT (*Stereotactic Body Radiation Therapy*)).
2. The duration of CR must have been confirmed with at least 2 consecutive imaging tests, without having a limit in the duration of this response. Although the patient had progressed subsequently, he/she may be included in this registry.
3. Patients from any risk group
4. Tumours of any histology

The doctor responsible for the patient, in the event that he/she continues to attend routine reviews at the hospital, undertakes to send the patient a privacy alert according to the new EU legislation on personal data: regulation 2016/679 of the European parliament.

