4.1.1. Inclusion Criteria

Patients must meet all the inclusion criteria below to be eligible for inclusion in the study:

[figure not shown]
1. Patients aged 18 years or older who have been treated for a metastatic renal carcinoma with first-line sunitinib in (prior cytokine treatment is admitted) between 2007 and October 30, 2018 and have obtained, as best response to treatment, total disease remission in the opinion of the treating physician from the clinical, radiological and/or macroscopic standpoint. This response must have been achieved through two possible strategies:
 - a. Systemic treatment with Sunitinib alone.
 - b. Treatment with Sunitinib and subsequent local treatment for one or several residual lesions that have not responded to the drug (traditional surgery, radiotherapy, SBRT (Stereotactic Body Radiation Therapy)).
2. The duration of the CR must have been confirmed by at least 2 consecutive imaging tests with no limit on the duration of this response. Patients with subsequent progression may be included in this registry.
3. Patients of any risk group.
4. Tumours of any histology.

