7.2 STATISTICAL ANALYSIS

7.2.1. Included and evaluable population

The descriptive statistics of patients who meet all the inclusion criteria and none of the exclusion criteria will be presented.

In the subpopulation of non-evaluable patients, their frequency distribution will be presented, depending on the reasons for non-eligibility:

[figure not shown]
- Patients who are not 18 years of age or older and who have been treated for metastatic renal carcinoma with Sunitinib as first-line (prior cytokine treatment is admitted) between 2007 and October 30, 2018.
- Patients aged 18 years or older who have been treated for a metastatic renal carcinoma with Sunitinib as second line.
- Patients aged 18 years or older who have been treated for a metastatic renal carcinoma with Sunitinib as first line (prior cytokine treatment is admitted) between 2007 and October 30, 2018 and who have not obtained, as best response to treatment, total disease remission in the opinion of the treating physician from the clinical, radiological and/or macroscopic standpoint.
- Patients whose duration of CR has not been confirmed with at least 2 consecutive imaging tests, with no limit on the duration of this response.
- Patients treated with another drug other than Sunitinib.
- Patients without radiology reports that substantiate the CR.
- Patients without a record of the dose and regimen of Sunitinib.
- Patients who achieved complete remission after October 30, 2018.

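### CR is an entry criterion, so the aim of finding factors linked to the occurrence of CR, or predictors of response, cannot be met; only timing, duration and type of response among responders can be studied

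*SAP*

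**What the plan says.** **Objective.** Protocol 7.1 lists as a primary objective "To look for associations between CR from a macroscopic point of view and the baseline characteristics of both the patient and the tumour". The abstract (Protocol 3) has the same aim with clinical in place of macroscopic, "To look for associations between CR from a clinical point of view and the baseline characteristics of both the patient and the tumour", and repeats the macroscopic form later on. SAP 2.2 carries the objective over and adds "The risk factors associated with the occurrence of CR from the macroscopic point of view will be sought". On the protocol title page, baseline characteristics "will be described in order to find predictive factors of response"; SAP 5 and 5.1 say much the same.

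**Who is analysed.** Protocol 8.2.1 admits patients "who have obtained as a best treatment response the total remission of the disease". SAP 2.1 defines the analysis population as patients "who have achieved a CR according to the criteria of the responsible medical team will be included", and SAP 4.1.1 requires that they "have obtained, as best response to treatment, total disease remission in the opinion of the treating physician". Both documents exclude patients without radiology reports supporting CR (Protocol 8.2.2, SAP 4.1.2). SAP 4.3 and 4.4 (other analyses, subgroups) are marked not applicable.

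**Patients without CR.** SAP 7.2.1 lists those "who have not obtained, as best response to treatment, total disease remission in the opinion of the treating physician" among the reasons for non-eligibility. Only the frequency of each reason is reported.

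**Analyses.** SAP 7.2.4 plans bivariate tests, Kaplan-Meier estimates, log-rank tests of baseline variables against time to CR, and a multivariable Cox model. SAP 3.2 sets significance at p<0.05.

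**The concern.** An association between a baseline factor and the occurrence of an outcome needs patients with and without that outcome. Here the outcome is the ticket of entry. The occurrence sentence and the predictive-factor labels therefore promise a result that the data cannot contain, and part of that promise sits in the primary objective.

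The risk is in the report. Hazard ratios for time to CR, computed in responders only, could be presented as predictors of response. A clinician would take that as information on which patients starting sunitinib are likely to reach CR. Protocol 8.9, which lists limitations, mentions the uncertain number of cases and missing data but not this.

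**Working it through.** **1. The plan's own figure.** The expected 90 or so cases (Protocol 8.5, SAP 4.1) are a feasibility estimate. Protocol 8.5 says no sample size calculation is needed, so there is nothing to reproduce. The check is structural.

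**2. The association in the analysis set.** For any baseline factor X, P(CR | X = 1) = P(CR | X = 0) = 1. The risk difference is 1 − 1 = 0 by construction. The odds are 1/0 in both groups, so the odds ratio is undefined. More patients would not change this.

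**3. Whether the mix of responders helps.** Let r be the CR rate among treated patients, s the share of responders with the factor, and q its prevalence among treated patients. Then P(CR | X = 1) = r·s/q and P(CR | X = 0) = r·(1 − s)/(1 − q). Take r = 3.6% from the Czech registry in Protocol 6 (100 of 2,803), and assume s = 50%.

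- q = 30% (assumed): 6.0% v 2.57%; odds ratio (0.060/0.940)/(0.0257/0.9743) = 2.42
- q = 50% (assumed): 3.6% v 3.6%; odds ratio 1.00
- q = 70% (assumed): 2.57% v 6.0%; odds ratio 0.41

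The same responders fit a harmful, null or favourable factor. The registry does not collect q.

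**4. The planned analyses, one by one (SAP 7.2.4).**

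- Bivariate tests: run in the CR-only set, so they can compare responders with one another.
- Log-rank test: the outcome is time to CR, and the stated conclusion concerns a shorter time to response. That wording is right.
- Cox model: labelled CR/PFS, with the outcomes then given as time to remission or to progression. Both are estimable in responders, but the covariates are called predictive factors of response.

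**5. Why time to CR does not stand in for likelihood of CR.** These are illustrations under assumed exponential times among responders.

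- A factor doubles the CR probability from 2% to 4%, odds ratio (0.04/0.96)/(0.02/0.98) = 2.04, with equal timing in responders. The responder-only hazard ratio is 1 in theory; a large simulation gave 0.98.
- A factor halves it from 4% to 2%, odds ratio 0.49, but shortens the median time to CR from 12.6 months (the TKI-only figure in Protocol 6) to an assumed 8. The hazard ratio is 12.6/8 = 1.58; the simulation gave 1.57. The direction is opposite.

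**6. The missing denominator.** At the CR rates cited in Protocol 6, 90 responders correspond to 90/0.01 = 9,000 treated patients (sunitinib expanded access), 90/0.036 = 2,500 (Czech registry) or 90/0.061 = 1,475 (pooled prospective studies). No baseline data are planned for the rest.

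**The case against.** The strongest defence is that the study calls itself purely descriptive and states no hypothesis, that the log-rank conclusion is already worded correctly, and that CR in the objective can be read as features of the response. Much of this stands. CR type (sunitinib alone, or with local treatment) and CR duration vary among responders, as does time to CR. A reader might infer that no planned analysis can relate a baseline factor to CR in any sense; the documents do not support that. The impossibility concerns occurrence only. But SAP 2.2 uses the word occurrence, and the absence of a hypothesis does not make a constant outcome informative.

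Three other inferences also go too far:

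- That the Cox outcome is left undefined. The sentence after the CR/PFS label defines it.
- That the bivariate tests take CR, yes or no, as their outcome. That sentence concerns events of a continuous nature. Complete remission is listed later, for the Kaplan-Meier analyses.
- That the SAP misstates the median when it says remission has occurred in 50% of patients. The analysis set consists of responders, so the statement is literally true of that set. It is only open to misreading.

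It can also be argued that deleting the occurrence sentence and qualifying the labels would be enough, because time to CR and PFS are secondary outcomes. That is a fair point on cost, but the wording of the primary objective would remain ambiguous.

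**Conclusion.** Wrong as written, and repairable by wording. The occurrence objective in SAP 2.2, the primary-objective wording when read as occurrence, and the predictive-factor labels on the protocol title page and in SAP 5, 5.1 and 7.2.4 cannot be met by any planned analysis. This follows from the entry criteria alone and needs no model.

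The size is categorical: nothing about the likelihood of CR is estimable. The odds ratios and hazard ratios above are illustrations under assumed inputs. They show that responder-only results need not agree with the true association, even in direction. They do not show that a reversal is likely in this registry, and should not be quoted as its expected error.

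The descriptive objectives, the analyses of time to CR and PFS after CR as responder-only analyses, and the recommendations for patients already in CR are not affected by this point.

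**What to change.** 1. Delete the occurrence sentence in SAP 2.2.
2. In the protocol title-page objectives, the abstract (both places) and 7.1, and in SAP 2.2, 5, 5.1 and 7.2.4, replace the association-with-CR and predictive-factor wording with: *baseline factors associated with time to CR, PFS after CR and other characteristics of the response (for example CR type or duration) among patients who achieved CR*.
3. State in those places and in Protocol 8.9 that, because only responders are included, no conclusion will be drawn on the likelihood of CR or on predictors of achieving it.
4. As clarifications only, in SAP 7.2.4 write *time to CR and PFS after CR* for CR/PFS, and say that the median refers to 50% of the patients who achieved CR.

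The cost is a less ambitious primary objective, in which time to CR and PFS, now secondary outcomes, become part of the association aim. A protocol amendment follows, since Protocol 8.7 requires one for major changes to the primary objective. No new data are needed. Keeping the occurrence aim would require a comparison group of treated patients without CR, which is a different study.
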